5.1.1 Treatment Phase

After informed consent has been provided, screening has been performed and participant eligibility confirmed, subjects will be admitted to the study site and randomized to one of three following treatments in a 1:1:1 ratio:

- *Rapamycin cream, topical* (0.5% rapamycin)
- *Rapamycin cream, topical* (1.0% rapamycin)
- Placebo cream

Patients will be instructed to apply the randomized treatment to the affected area once a day in the evenings (i.e. before retiring) for 26 weeks.

5.2 Investigational Products

The investigational products have been manufactured by Sterling Pharmaceuticals Services, LLC in its GMP approved manufacturing facility. Sterling Pharmaceutical Services holds a valid GMP issued by the USFDA (Establishment Identifier No. 3009705561).

Lab scale batches of both strengths of *Rapamycin cream, topical* have been shown to be stable under room temperature conditions (25°C/60%RH) for at least 12 months. It is expected that the study drug will be stable long term under these conditions and stability studies are ongoing. Re-testing of the samples of the remaining study drugs will be conducted at the end of the study to confirm that the product is compliant with stability specifications.

The study drugs are contained in aluminum tubes with screw caps. Each 35 g tube contains 30 g of the study drug.

The study drug supplied for use in this study is to be prescribed only by the principal investigator or named co/sub-investigators and may not be used for any purpose other than that outlined in this protocol. Neither the investigators nor any designees may provide study drug to any patient not participating in the study.

The investigator or pharmacy designee will maintain an inventory record of study drug dispensed to assure regulatory authorities and the Sponsor that it has not been dispensed to any person who is not a participant under the terms and conditions set forth in this protocol.

At the termination of the study, all unused study drug (once it has been inventoried and accountability documents have been reviewed by the assigned study monitor) will be destroyed, and a destruction certificate will be issued by a licensed destruction company.

5.3 Randomization

Randomization will occur at the study site once participant eligibility is confirmed, up to two weeks before the first clinical visit (V0), which includes the first application of the study drug. Participants

will be randomly assigned to one of three possible treatments in a balanced fashion (i.e. 1:1:1 ratio). Each successive subject will receive a unique study randomization number which includes both a two-digit site prefix (e.g. 01), a single-digit age stratum identifier (e.g. 0) and two-digit subject identifier (e.g. 01). For example, the first patient in the first stratum (age group: 6 – 11 years) at site #1 will be assigned the randomization number 01-001. Randomization will be balanced by using permuted blocks and stratified by site and age group (6 – 11 years; 12 – 17 years; 18 – 65 years). Participants will be enrolled into the study until a minimum of 120 participants are randomized and have started using study drug.

The randomization sequence will be computer-generated by the study statistician prior to any enrolment. The statistician will maintain a confidential schedule of participant IDs and treatment allocations. The dispensing pharmacist at each site will not be blinded, and will maintain a confidential schedule of participant IDs and treatment allocations for participants at their site. The pharmacist will be responsible for over-labelling the study medication. The randomization sequences will be maintained by the site pharmacist in a secure location which cannot be accessed by other staff members involved in the conduct of the trial.

The sites will receive a set of sealed blinding envelopes for emergency un-blinding, with a separate envelope for each participant number. The principal investigator will be the first point of contact should the randomization code need to be broken for an individual participant during the study. The emergency unblinding envelopes for each participant should only be opened in an emergency when knowledge of the study drug may affect the management of the patient.

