6 STUDY DATA AND ENDPOINTS

6.1 Efficacy data

6.1.1 Primary Efficacy Endpoint

At screening, each visit (V1-V5) and at follow-up a blinded dermatologist will grade each patient's lesion using the Investigator's Global Assessment (IGA) of facial angiofibroma severity developed by the sponsor and created solely to identify the response of a treatment in FA associated with TSC.

Table 2: IGA scoring of Facial Angiofibroma Lesions

Grade	Short Description	Detailed Description
0	Clear	No signs of facial angiofibroma
1	Almost Clear	Few small angiofibromas (< 2 mm); normal to pink coloration in affected area*
2	Mild	Predominantly small angiofibromas (< 2 mm) with few intermediate tumors (2-4 mm); pink to red coloration in affected area
3	Moderate	Predominantly intermediate angiofibromas (2-4 mm) with few large tumors (> 4 mm); red coloration in affected area
4	Severe	Mix of intermediate (2-4 mm) and large angiofibromas (>4 mm) present diffusely on face; intense and generalized redness on the whole face

* Note: coloration refers to both the FA lesions and the background facial skin tone
Where lesion size and coloration are discrepant within the grade, emphasis should be placed on lesion size.

The primary efficacy endpoint is the percentage of patients obtaining successful treatment, based on the blind assessment using the IGA scale after 26 weeks or at discontinuation/withdrawal. Success is defined as clear or almost clear with an improvement of at least two grades from baseline, i.e. 2 to 0; 3 to 1.

To the extent possible, the same Investigator should conduct all IGA assessments per patient at each site throughout the study.

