10.3 Statistical Analyses

10.3.1 Primary Efficacy Endpoint

The data for the primary endpoint, the percentage of patients obtaining successful treatment based on the blind assessment using the IGA scale after 26 weeks or at last visit if early withdrawal/discontinuation, will be summarized by treatment group. Success is defined as clear or almost clear with an improvement of at least two grades from baseline, i.e. 2 to 0; 3 to 1. Statistical analysis of the primary endpoint will be performed using a logistic regression model which will include treatment effect and stratum as fixed factors and baseline IGA score as a covariate. This model will be used to generate the odds ratios and 95% confidence intervals of the individual dose treatments compared with placebo, with the p-values for these comparisons adjusted using the Holm-Bonferroni adjustment.

An exploratory analysis will compare the two active groups in the same manner as the primary endpoint, with no adjustment for multiple comparisons. This analysis will be summarized with the Odds ratio and 95% confidence interval.

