10.3.2 Secondary Efficacy Endpoints

The time-to-treatment success will be summarized using Kaplan-Meier analyses and compared between each dose group and placebo using the stratified log-rank test. The secondary endpoints change in IGA and FASI from baseline to 26 weeks/last assessment, and objective and subject improvement from baseline to 26 weeks/last assessment, will be summarized by treatment group using means, medians, standard deviations, interquartile ranges and minima and maxima. These changes will be analyzed using ANOVA including treatment and stratum as main effect fixed factors, with planned pairwise comparisons between each dose group and placebo. If the data is not adequately normally distributed the Kruskal-Wallis non-parametric ANOVA, and Mann-Whitney U tests comparing changes between treatment groups will be used for the analysis. Baseline for the IGA and FASI scores is defined as the last pre-treatment assessment, whether obtained at screening, randomization or V0.

Categorical Improvement scores will be compared amongst study groups using the Kruskal-Wallis non-parametric ANOVA, and Mann-Whitney U tests comparing changes between each dose group and placebo.

The type I error rate associated with the testing of the six secondary endpoints will be strictly controlled using the Hochberg procedure. This will involve ranking the 6 p-values derived from the testing of each dose group with placebo from highest to lowest. If the highest p-value is <0.05 , then all six comparisons are considered statistically significant if not significant then the next highest is tested at $p=0.025$. The p-value continues to reduce at each non-significant step based on the Bonferroni adjustment.

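### Site is a randomization factor but no efficacy model names it; if *stratum* in the secondary ANOVA means age group alone, standard errors are somewhat too wide and some power can be lost

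*Combined protocol and SAP*

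**What the plan says.** Section 5.3 (Randomization): "Randomization will be balanced by using permuted blocks and stratified by site and age group", with three age groups. The randomization number has a two-digit site prefix, then "a single-digit age stratum identifier". The worked example speaks of "the first patient in the first stratum (age group: 6 – 11 years) at site #1". In that section *stratum* therefore labels the age group, and site is named apart from it.

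Section 10.3.2, on change in IGA, change in FASI and the objective and subjective improvement ratings: "These changes will be analyzed using ANOVA including treatment and stratum as main effect fixed factors". The synopsis has the same sentence. The fallback is "If the data is not adequately normally distributed the Kruskal-Wallis non-parametric ANOVA, and Mann-Whitney U tests", with no stratum or site attached. Section 10.3.1 uses the same word for the primary logistic model, "which will include treatment effect and stratum as fixed factors and baseline IGA score as a covariate". Section 10 does not define it. Site is named only in 10.3.4, as a subgroup for informational summaries of the primary endpoint.

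On raters, 6.1.1 says that "the same Investigator should conduct all IGA assessments per patient at each site", where feasible. Section 6.1.2 asks the same for FASI and for the clinician's improvement rating. The subjective rating comes from the patient or the parent/caregiver.

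**The concern.** Blocking on site balances the arms within sites, so site differences largely drop out of the treatment contrast. If the model then omits site, the same differences still count as residual variance. The reported standard error exceeds the true sampling SD of the estimate, and the test runs below its nominal level.

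Site differences are plausible. IGA, FASI and the clinician rating are graded at the patient's own site, 4.1 places sites in the United States, Europe and Australasia, and 10.2 says this IGA scale is being used for the first time. At stake is precision on four of the six secondary endpoints. There is also a reproducibility problem: with *stratum* undefined, two statisticians could fit different models to the same data.

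**Working it through.** **1. The plan's own figure.** Section 10.2 gives 40 per group for 10% versus 40%, alpha 0.025 (taken as two-sided), power above 80%.

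n = [z(0.9875)·√(2·0.25·0.75) + z(0.80)·√(0.09 + 0.24)]² / 0.30² = (2.241·0.612 + 0.842·0.574)² / 0.09 = 38.3, so 39. Power at 40 is 82.0%.

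The figure reproduces. It concerns the primary endpoint; the plan states no power for the secondary ANOVA, so what follows rests on assumptions.

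**2. Ideal case.** Let ρ be the share of outcome variance that lies between sites. With perfect balance within site, omitting site multiplies the standard error by 1/√(1 − ρ). Take the effect that gives 80% power without site at 40 per arm and two-sided 0.05: (1.960 + 0.842)·√(2/40) = 0.63 SD. Power with site in the model is then Φ(2.802/√(1 − ρ) − 1.960).

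| ρ | SE ratio | Power with site |
|---|---|---|
| 0.05 | 1.026 | 82.0% |
| 0.10 | 1.054 | 84.0% |
| 0.20 | 1.118 | 88.0% |

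**3. Realistic blocks.** Blocks in small site-by-age cells are often incomplete, so balance is imperfect. Simulation: 120 patients, uneven sites, three age groups, blocks of 6, total variance 1. Entries are standard errors of one dose-versus-placebo contrast.

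| Sites | ρ | Age only, reported | Age only, true | Random site (ρ known) | Site-by-age cells |
|---|---|---|---|---|---|
| 10 | 0.05 | 0.2240 | 0.2206 | 0.2201 | 0.2316 |
| 10 | 0.10 | 0.2236 | 0.2167 | 0.2150 | 0.2257 |
| 10 | 0.20 | 0.2220 | 0.2079 | 0.2031 | 0.2125 |
| 30 | 0.05 | 0.2263 | 0.2245 | 0.2238 | 0.2842 |
| 30 | 0.10 | 0.2255 | 0.2218 | 0.2196 | 0.2753 |
| 30 | 0.20 | 0.2255 | 0.2179 | 0.2107 | 0.2598 |

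Reported over true for the age-only model: with 10 sites 0.2240/0.2206 = 1.015, then 1.032 and 1.068; with 30 sites 1.008, 1.017 and 1.035. At ρ = 0 the excess is zero.

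**4. Power with the site variance estimated.** Two separate simulations fitted REML with age group fixed and a random site intercept. Both used 120 patients and blocks of 6, with 2,000 trials per setting under the alternative. One took an effect of 0.63 SD with 8, 15, 20 or 30 sites; the other took 0.6 SD with 8, 15 or 30 sites. Gain in power over the age-only ANOVA, in percentage points:

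| ρ | First | Second |
|---|---|---|
| 0 | 0.1–0.7 | not quoted |
| 0.05 | 0.6–1.3 | about 1 (ρ 0.03–0.05) |
| 0.10 | 2.1–2.6 | 2–3.5 |
| 0.20 | 4.4–5.8 | 5.5–6 |

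In the first simulation the random-site model lost power in none of 20 settings. Its type I error was 4.3–5.9% (simulation error about 0.5 points), against 3.4–3.7% for age-only at ρ = 0.20.

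**5. The other reading.** With S sites there are up to 3S site-by-age cells: 30 cells for 10 sites (120/30 = 4 patients per cell) and 90 for 30 sites (120/90 = 1.3). From the table at ρ = 0.05, the cell model's standard error exceeds the random-site one by 0.2316/0.2201 = 1.05 with 10 sites and 0.2842/0.2238 = 1.27 with 30. In the latter setting simulated power is 59.2%, against 79.0% for age-only.

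**The case against.** - **The ANOVA may already contain site.** A reader might infer from 5.3 that the model certainly carries age group only. The documents do not settle this: section 10 leaves the word undefined, and in a design stratified by two factors a stratum is often a cell of both. This stands, so the age-only consequence is conditional. The cell reading is no rescue, as step 5 shows.
- **Power need not be lost.** A reader might take the loss as a fact. It depends on a site share and site count that the documents do not give. How site enters also matters: with fixed site effects, 20 to 30 sites and a site share of 0.10 or less, simulated power falls by 2 to 7 points (30 sites, share 0.05: 79.0% to 72.3%). This stands against fixed site effects, but not against a random intercept.
- **The rater argument is narrower than it looks.** The plan asks for one assessor per patient, not one per site. If that assessor scores both baseline and week 26, a constant shift largely cancels in change in IGA and FASI. The cancellation does not help the clinician's percentage rating, which is given directly at each visit. The subjective rating has no site rater. All of this stands and points to the low end of the range for the two change scores.
- **The rank tests may be used instead.** Entry is limited to IGA 2 or 3, so change in IGA takes few values and the fallback is a real prospect. It carries no stratum at all. This stands, and the fix has to cover it.
- **False positives or the primary analysis.** A reader might fear either. Omitting site makes these tests conservative, and the figures here concern linear models; they do not carry over to the logistic regression in 10.3.1.

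**Conclusion.** The point holds in a conditional form. What is firm is that site is a randomization factor, no efficacy model names it, and the *stratum* in the secondary ANOVA is undefined. On the reading that 5.3 favours, reported standard errors are about 1% to 7% above the true sampling SD for site shares of 0.05 to 0.20 and 10 to 30 sites. The power given up against a random site intercept is about 0 to 1 point at a share of 0.05 or less, 2 to 3.5 at 0.10 and 4 to 6 at 0.20. These figures assume 8 to 30 sites, blocks of 6, an effect near 0.6 SD and one unadjusted two-sided 5% comparison. Inference stays valid. Priority is minor to moderate.

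**What to change.** In 10.3.2 and the synopsis, replace *stratum* in the ANOVA sentence with age group as a fixed effect plus site as an additive random intercept, not crossed with age group. State REML and the degrees-of-freedom method, since the simulated type I error of the mixed model scattered up to 5.9%. Make the rank-based fallback a stratified test, for example van Elteren. Name its strata and say how sites too small to hold both arms are pooled. Define *stratum* wherever else section 10 uses it, so that each model can be reproduced, and settle this before unblinding.

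The cost is a few sentences and a mixed model in place of a simple ANOVA. It needs no new data and no extra patients, and in the simulations it lost no power when site had no effect. The gain from the stratified rank test was not quantified here.

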5.4 Blinding

Double-blinding will be achieved by the use of a vehicle placebo cream that has the same composition as *Rapamycin cream, topical*, but does not contain any active ingredient (rapamycin). The placebo cream and *Rapamycin cream, topical* are visually indistinguishable and are packaged into identical aluminum 30 g (net) tubes. Patients and treating and assessing dermatologists will all be blind to randomized treatment.

5.5 Prohibited concomitant medications

The following medications are prohibited after enrolment in this trial due to the risk of interference in the evaluation of efficacy/safety:

- Laser and surgical treatment of the target treatment area
- Administration of mTOR inhibitors (rapamycin/sirolimus, everolimus, temsirolimus etc.)
- Application of steroidal or antibacterial agents to the target area
- Administration of cyclosporine or macrolide antibiotics

- Strong inhibitors of CYP3A4 and/or P-gp (such as ketoconazole, voriconazole, itraconazole, erythromycin, telithromycin, or clarithromycin) or strong inducers of CYP3A4 and/or P-gp (such as rifampin or rifabutin)

While not prohibited, concomitant use of rapamycin with some medications may increase the risk of certain adverse events. The following precautions will be taken:

- Patients taking drugs known to cause angioedema, such as angiotensin-converting enzyme (ACE) inhibitors, will be closely monitored as concomitant use of rapamycin may increase the risk of developing angioedema.
- Patients taking statins and/or fibrates will be monitored for the possible development of rhabdomyolysis and other adverse effects, as described in the respective labelling for these agents.

5.6 Treatment compliance

The nightly administration of study medication will be documented by the patient or caregiver in the patient diary. A clinical trial monitor will review patient source documents, drug accountability records and patient diaries on an ongoing basis to assess treatment compliance. Additionally, returned tubes will be weighed to determine the amount of study medication used by the participant.

Acceptable compliance is no more than an average of one missed dose per week (26 missed doses over the course of the study) and no more than seven missed consecutive doses.

6 STUDY DATA AND ENDPOINTS

6.1 Efficacy data

6.1.1 Primary Efficacy Endpoint

At screening, each visit (V1-V5) and at follow-up a blinded dermatologist will grade each patient's lesion using the Investigator's Global Assessment (IGA) of facial angiofibroma severity developed by the sponsor and created solely to identify the response of a treatment in FA associated with TSC.

Table 2: IGA scoring of Facial Angiofibroma Lesions

Grade	Short Description	Detailed Description
0	Clear	No signs of facial angiofibroma
1	Almost Clear	Few small angiofibromas (< 2 mm); normal to pink coloration in affected area*
2	Mild	Predominantly small angiofibromas (< 2 mm) with few intermediate tumors (2-4 mm); pink to red coloration in affected area
3	Moderate	Predominantly intermediate angiofibromas (2-4 mm) with few large tumors (> 4 mm); red coloration in affected area
4	Severe	Mix of intermediate (2-4 mm) and large angiofibromas (>4 mm) present diffusely on face; intense and generalized redness on the whole face

* Note: coloration refers to both the FA lesions and the background facial skin tone
Where lesion size and coloration are discrepant within the grade, emphasis should be placed on lesion size.

The primary efficacy endpoint is the percentage of patients obtaining successful treatment, based on the blind assessment using the IGA scale after 26 weeks or at discontinuation/withdrawal. Success is defined as clear or almost clear with an improvement of at least two grades from baseline, i.e. 2 to 0; 3 to 1.

To the extent possible, the same Investigator should conduct all IGA assessments per patient at each site throughout the study.

6.1.2 Secondary and Exploratory Efficacy Endpoints

The following *secondary* efficacy endpoints will be derived from IGA scores:

1. Time to treatment success
2. Change from baseline in IGA after 26 weeks treatment or at last visit if early withdrawal/discontinuation

In addition, the following *exploratory* efficacy endpoint will be derived from IGA scores:

1. The percentage of patients with successful treatment according to IGA scale after 2, 8, 14 and 20 weeks treatment
2. Change from baseline in IGA after 2, 8, 14 and 20 weeks treatment
7. Change in IGA from week 26 to Follow-up (4 weeks after final dose)

Lesion severity will also be graded using the Facial Angiofibroma Severity Index (FASI) [Appendix 2: Facial Angiofibroma severity index (FASI)]. Using the FASI, lesions are graded according to their erythema, size and extent. Erythema is scored from 0 to 3 and lesion size are scored from 0 to 3, while extent carries greater specific weight (scored from 2 to 3), as the scale's developers consider the lesion's extent to be a fundamental factor in estimating the degree of severity.

The FASI is obtained by summing the partial scores assigned to each of three relevant features of FA for a maximum score of 9. FASI was first described in a clinical trial of 9 months duration (33) and the reliability and validity was subsequently reported (16). This will provide data for the following *secondary* efficacy endpoint:

3. The change in FASI from baseline after 26 weeks treatment or at last visit if early withdrawal/discontinuation

In addition, the following *exploratory* efficacy endpoints will be derived from FASI scores:

3. Change from baseline in FASI after 2, 8, 14 and 20 weeks treatment
4. Change from baseline in each FASI component (erythema, size, extension) after 2, 8, 14, 20 and 26 weeks treatment
8. Change in FASI from week 26 to Follow-up (4 weeks after final dose)

To the extent possible, the same Investigator should conduct all FASI assessments per patient at each site throughout the study.

At Visits 1-5 patients or their parents/caregivers (for patients under the age of 18) will be asked to estimate the percentage improvement in the FA lesion appearance from their perspective since baseline (V0) [Appendix 3: Subjective and Objective Improvement Ratings]. Similarly, the investigators will estimate the percentage improvement from a clinical perspective. Improvement will be defined as: minimal <30%, moderate 30-59%, good 60-89%, excellent >90%. This is similar to the objective and subjective improvement ratings used by Foster et al. (23) and Tu et al. (37). This will provide data for the following *secondary* efficacy endpoints:

4. Subjective improvement rating (minimal, moderate, good or excellent) in facial angiofibroma from first visit (V0) after 26 weeks of treatment or at last visit if early withdrawal/discontinuation
5. Objective improvement rating (minimal, moderate, good or excellent) in facial angiofibroma from first visit (V0) after 26 weeks of treatment or at last visit if early withdrawal/discontinuation

In addition, the following *exploratory* efficacy endpoints will be derived from percentage improvement scores:

5. Subjective (patient or parent/caregiver) improvement rating from first visit (V0) after 2, 8, 14 and 20 weeks treatment
6. Objective (clinician) improvement rating from first visit (V0) after 2, 8, 14 and 20 weeks treatment

To the extent possible, the same clinician should conduct all improvement rating assessments per patient at each site throughout the study. Similarly, the same person (patient or parent/caregiver) should report all improvement rating assessments throughout the study.

Upon completion of the double-blind treatment phase, patients or their parents/caregivers (for patients under the age of 18) will be asked which of the following statements they agree with:

- 3: I got significantly better on the treatment
- 2: I got moderately better on the treatment
- 1: I got slightly better on the treatment
- 0: The treatment made no difference
- -1: I got worse on the treatment

This is similar to the subjective improvement rating used by Koenig et al. (47). See also Appendix 4: Categorical improvement of Facial Angiofibroma. This will provide data for the following *secondary* efficacy endpoint:

6. Categorical Improvement of Facial Angiofibroma from first visit (V0) after 26 weeks treatment

Photographs of the FA lesions will be taken at randomization, and V1-5 and at follow-up to document changes. These will not be used directly for any efficacy endpoints, but will be available for auditing purposes.

